6.1.3.2 Clinical laboratory values

Hematology, blood chemistry, urinalysis and immunogenicity values are recorded at baseline for screening, 30 ± 3 days post IP administration and following any adverse events. Descriptive statistics including shift tables will be generated for all laboratory tests performed i.e. the actual values and the changes from pre-injection.

Data listing will be ordered by subject and measuring time. Listings of abnormal results (both clinically and non-clinically relevant) will also be reported.

6.1.3.3 Vital signs and physical examination

Vital signs and physical examination data are recorded once at screening visit and twice at imaging visit (SPECT/CT Visit, Day 0), before the injection of ^{99m}Tc-rhAnnexin V-128 and at the end of SPECT/CT (after the ^{99m}Tc-rhAnnexin V-128 injection). Descriptive statistics will be tabulated by measuring time for raw data and changes from baseline. Data listings will be ordered by subject and measuring time.

6.1.4 Missing data and outliers

6.1.4.1 Missing data

As stated in the protocol, missing data will not be replaced.

6.1.4.2 Missing or incomplete dates

Incomplete dates due to missing day will be recorded as full dates replacing the missing day with the first day of month (01). Incomplete dates due to missing day and month will be recorded as full dates replacing the missing day and month with the first day of month and first month of the year (01/January). The trial database will record the information about incomplete dates due to missing day or due to missing day and month.

Version: 01 Page: **28 of 167**

Only the incomplete dates related to medical history (date of diagnosis and end date), concomitant medications (start and end date) and AEs (start and end date) will be replaced according to the above rule.

Calculation, sorting or assignation based on dates, in case of incomplete dates, will be performed using the related full dates defined by the above rule.

In all listings, missing dates will be missing and incomplete dates will be reported as full dates. In all listings will also be reported the information about incomplete dates according to the following coding: missing value = full date, Day = missing day, Day&Month = missing day and month.

6.1.4.3 **Outliers**

For categorical or score data, like adverse events, physical exam's findings and disease assessment parameters, outliers are not expected.

Demographic, vital signs, and clinical laboratory (hematology, blood chemistry and urinalysis) parameters will be checked for outliers according to data plausibility, normal ranges and the range between mean ± 2 S.D.

For each identified outlier, will inform the Sponsor in order to assess any errors. If data cannot be verified or if relevant, the descriptive statistics of the related parameters will be reported with and without the outliers. If appropriate, outliers can also be specifically identified in the boxplots.

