12.5.1 Adverse Events / Serious Adverse Events

All original AE/SAE terms will be coded using the Medical Dictionary for Regulatory Activities (MedDRA). System organ classes and preferred terms will be used in the analyses. The type and incidence of AEs/SAEs, as well as severity and relatedness to the investigational product will be tabulated.

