6.1.3.1 Adverse events

All original AE/SAE terms will be coded using the Medical Dictionary for Regulatory Activities (MedDRA) Version 19.0.

Adverse events (AEs) will be listed on an individual basis, including relationship and severity, LLT (Lowest Level Term) and verbatim term. Treatment emergent Adverse events (TEAEs) and Adverse Drug Reactions (ADRs) will be summarized by System Organ Class (SOC) and Preferred Term (PT), grouping patients versus control subjects, and also including a total column for all subjects who received Annexin. Participants with more than one adverse event within a particular SOC and PT will be counted only once for that SOC and PT reporting the highest level in severity. The incidence of TEAEs and ADRs will also be summarized by subject type and severity.

Listings and summaries of serious adverse events (SAEs), adverse events leading to withdrawal and listings of deaths will also be presented.

Treatment Emergent Adverse Events and Adverse Drug Reactions will be defined as below:

Version: 01 Page: **27 of 167**

- Treatment Emergent Adverse Events: Events that emerge after the ^{99m}Tc-rhAnnexin V-128 injection and up to 30 days after the injection that were absent before it or worsen relative to the pre-treatment state.
- Adverse Drug Reactions: Treatment emergent adverse events possibly or probably related to study treatment.

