Version: 01 Page: **58 of 167**

Listing 16.2.7.1/1: All Adverse Events

				Primary system			Study day of				
Subject ID	Subject group*	Event ID	Event description	organ class	Preferred term	Lowest level term	onset (days)§	Ongoing?	Duration (days)	TEAE [^]	
PAT_PATNUMBER	PAT_INFCONS_TYPE	ID_WEB	AE_NAME	MEDDRA_SOC	MEDDRA_PT	MEDDRA_LLT	[Derived data]	AE_ONGOING_YN	[Derived data]	[Derived data]	
04-CA-001	Patient	XXX	XXXXXX	XXXXXX	XXXXXXXX	XXXXXXX	YY	No	YY	Yes	
04-CA-002	Control	XXX	XXXXXX	XXXXXX	XXXXXXXX	XXXXXXX	YY	No	YY	Yes	
04-CA-003	Control	XXX	XXXXXX	XXXXXX	XXXXXXXX	XXXXXXX	YY	Yes	YY	Yes	

Note: NA = Not Available

^ TEAE: Treatment Emergent Adverse Event as defined in paragraph 6.1.3.1

^{*} Patient = Subject with asymptomatic plaque; Control = Healthy volunteer

[§] Study day of onset is defined as days from Annexin injection

Version: 01 Page: **59 of 167**

Listing 16.2.7.1/2: All Adverse Events

Subject ID	Subject group*	Event ID	Event description	AE caused premature withdrawal?	SAE	SAE seriousness	Maximal severity	Causal relationship with medication or procedure	Possible cause	Specify other possible cause	TEAE^
PAT_PATNUMBER	PAT_INFCONS_TY PE	ID_WEB	AE_NAME	AE_WITHD_YN	AE_SAE_YN	[Derived data]	AE_MAXSEV	AE_REL	AE_CAUSE	AE_CAUSE_SP	[Derived data]
04-CA-001	Patient	XXX	XXXXXXX	Yes	Yes	XXXXXX / XXXXX	Grade 2 (Moderate)	Possible	Other	XXXXXXXXX	Yes
04-CA-002	Control	XXX	XXXXXXX	No	No	XXXXXX / XXXXX	Grade 1 (Mild)	Unlikely	Pre-existing/ underlying disease	XXXXXXXXX	Yes
04-CA-003	Control	XXX	XXXXXXX	No	No	XXXXXX / XXXXX	Grade 3 (Severe)	Unrelated	Other treatment	XXXXXXXXX	Yes

Data Source Table: W_PATIENT, W_AE.

Note: NA = Not Available

^{*} Patient = Subject with asymptomatic plaque; Control = Healthy volunteer

[^] TEAE: Treatment Emergent Adverse Event as defined in paragraph 6.1.3.1

Confidential

Version: 01 Page: **60 of 167**

Listing 16.2.7.1/3: All Adverse Events

Subject ID	Subject group*	Event ID	Event description	Action taken	Other action taken	Other action taken, specify	Outcome	TEAE^
PAT_PATNUMBER	PAT_INFCONS_TYPE	ID_WEB	AE_NAME	AE_ACT	[Derived data]	AE_ACT_OTH_SP	AE_OUTCOME	[Derived data]
04-CA-001	Patient	XXX	XXXXXXX	No action	XXX/XXXXX/XXX		Resolved	Yes
04-CA-002	Control	XXX	XXXXXXX	Dose modification in next treatment	XXX/XXXXX	XXXXXX	Worsened	Yes
04-CA-003	Control	XXX	XXXXXXX	Unknown	XXX		Persisting	Yes

Data Source Table: W_PATIENT, W_AE.

Note: NA = Not Available

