Treatment emergent SAEs	n (%) [n. events]	99 (99.9) [99]	99 (99.9) [99]	99 (99.9) [99]
Treatment emergent serious adverse drug reactions	n (%) [n. events]	99 (99.9) [99]	99 (99.9) [99]	99 (99.9) [99]
Treatment emergent AEs leading to withdrawal	n (%) [n. events]	99 (99.9) [99]	99 (99.9) [99]	99 (99.9) [99]
Treatment emergent AEs leading to death	n (%) [n. events]	99 (99.9) [99]	99 (99.9) [99]	99 (99.9) [99]

Source: Data listings {Specify data listing number(s)} Analysis dataset: {Specify datasets}

Note: Format is number of subjects (percent of subjects) [number of events].

^{*} Patient = Subject with asymptomatic plaque; Control = Healthy volunteer

Version: 01 Page: **102 of 167**

Table 14.3.1.2: Number (%) of Subjects Reporting Treatment Emergent Adverse Events by Primary System Organ Class and Preferred Term – Safety Population

PRIMARY SYSTEM ORGAN CLASS PREFERRED TERM	STATISTIC	PATIENT* (N=xx)	CONTROL* (N=xx)	ALL SUBJECTS (N=xx)
Any adverse events	n (%)	99 (99.9)	99 (99.9)	99 (99.9)
System organ class 1	n (%)	99 (99.9)	99 (99.9)	99 (99.9)
Preferred term 1	n (%)	99 (99.9)	99 (99.9)	99 (99.9)
	n (%)	99 (99.9)	99 (99.9)	99 (99.9)
Preferred term m	n (%)	99 (99.9)	99 (99.9)	99 (99.9)
System organ class	n (%)	99 (99.9)	99 (99.9)	99 (99.9)
Preferred term 1	n (%)	99 (99.9)	99 (99.9)	99 (99.9)
	n (%)	99 (99.9)	99 (99.9)	99 (99.9)
Preferred term m	n (%)	99 (99.9)	99 (99.9)	99 (99.9)
System organ class m	n (%)	99 (99.9)	99 (99.9)	99 (99.9)
Preferred term 1	n (%)	99 (99.9)	99 (99.9)	99 (99.9)
	n (%)	99 (99.9)	99 (99.9)	99 (99.9)
Preferred term m	n (%)	99 (99.9)	99 (99.9)	99 (99.9)

Source: Data listings {Specify data listing number(s)} Analysis dataset: {Specify datasets} Dictionary Name: MedDRA Version: 19.0

Notes: All percentages are based upon the number of enrolled subjects by group.

Subjects with more than one event within a particular SOC and PT will be counted only once for that SOC and PT.

^{*} Patient = Subject with asymptomatic plaque; Control = Healthy volunteer

Version: 01 Page: **103 of 167**

Table 14.3.1.3: Number (%) of Subjects Reporting Treatment Emergent Adverse Events by Severity – Safety Population

PRIMARY SYSTEM ORGAN CLASS PREFERRED TERM	Gra (M	de 1 ild)	Grade 2 (Moderate)		Grade 3 (Severe)		Grade 4 (Threatening/ disabling)		Grade 5 (Death)		Missing		Total	
	Patient*	Control*	Patient*	Control*	Patient*	Control*	Patient*	Control*	Patient*	Control*	Patient*	Control*	Patient*	Control*

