12 APPENDICES TO THE SAP TEMPLATE

12.1 Derived data

The following derived data will be calculated and included in the listings or in the tables:

(1) Age

Subject age (years) will be derived as (informed conset date - birth date)/365.25 and truncated to the largest integer that is less than or equal to the calculated result. Since birth date is truncated (i.e. only month and year will be filled in the eCRF), it will be approximated using "01" as value for the day.

(2) **BMI**

BMI (kg/m²) will be automatically derived as [weight] (kg)/([height](cm)/100)² and rounded to the nearest decimal.

(3) Time from injection

Time from injection (min) will be derived as the difference between SPECT/CT scan time [SP_TIME/SPCT_TIME] and injection time [ANN_TIME].

(4) Adverse event duration

If the start and end dates of the adverse event are identical then "<1" day will be presented with the duration in hh:mm recorded in the eCRF if it is available. If times are available, the duration will be calculated as (end date/time - start date/time) and presented in days hh:mm. If at least one time is missing and if the duration is greater than 24 hours then it will be calculated as (end date - start date)+1 and presented in days. If the recorded end date is CONT. (for continuing), the end date will be listed as "ongoing" and the duration will be approximated as "≥(last attended visit date - start date)+1" day(s). If the start date or the end date are partial the duration will be presented as a superior inequality "≥ xx" day(s) (i.e. "≥2" where start date = 31JAN2004 and end date = FEB2004 or start date = JAN2004 and end date = 01FEB2004).

(5) Study day of onset

If the start date of the adverse event is identical to the date of injection, then "1" day will be presented with the time to onset in hh:mm recorded in the eCRF if it is available. If the date of onset is greater than the date of injection then it will be calculated as (start date - injection date+1) and presented in days. If the date of onset precedes the date of injection the study day will be calculated as (start date - injection date). If the start date is partial, the time since injection will be presented as a superior

Statistical Analysis Plan ANNEXIN 04

Confidential

Version: 01 Page: **167 of 167**

inequality (i.e. for an AE started in FEB2004 after the injection performed on 31JAN2004, the delay of onset will be "≥2" days).

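### SAP 6.1.4.2, read literally, dates some post-injection AEs with unknown onset day before injection and so outside the TEAE tables; separately, SAP 6.1.10 leaves long-standing ongoing drugs out of both medication tables

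*SAP*

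**What the plan says.** **AE dates.** SAP 6.1.4.2 states: "Incomplete dates due to missing day will be recorded as full dates replacing the missing day with the first day of month (01". If the month is missing too, the date becomes 1 January. The rule covers AE start and end dates, and any calculation, sorting or assignment that depends on a date "will be performed using the related full dates defined by the above rule". No exception is made for the month of injection.

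**TEAE and ADR.** SAP 6.1.3.1 defines TEAEs as "Events that emerge after the ^{99m}Tc-rhAnnexin V-128 injection and up to 30 days after the injection", provided they were absent before or have worsened. Adverse drug reactions (ADRs) are "Treatment emergent adverse events possibly or probably related to study treatment", so they are a subset of TEAEs. The TEAE column in the AE listings is a derived variable whose only reference is the footnote "TEAE: Treatment Emergent Adverse Event as defined in paragraph 6.1.3.1". SAP 12.1 (Derived data) has no TEAE entry.

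**AE tables.** All six rows of Table 14.3.1.1 are treatment-emergent, down to "Treatment emergent AEs leading to death". Tables 14.3.1.2 to 14.3.1.7 count only TEAEs, ADRs or their serious subsets. Protocol 12.5.1 asks for more: "The type and incidence of AEs/SAEs, as well as severity and relatedness to the investigational product will be tabulated". Protocol 13.1 collects AEs from consent.

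**Partial-date examples.** SAP 12.1(4) and (5) print durations and onset delays from partial dates as inequalities. One case, "start date = JAN2004 and end date = 01FEB2004", is given as ≥2 days.

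**Medications.** SAP 6.1.10 plans two tables. Table 14.1.7.1 takes drugs taken and stopped in the 30 days before injection. Table 14.1.7.2 takes drugs begun in those 30 days and continued past injection, plus drugs begun after injection.

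**The concern.** (a) Setting an unknown day to the 1st moves the onset as early as the known month allows. When that month is also the month of injection, an event that followed injection is placed before it. Because every AE frequency table is restricted to TEAEs or ADRs, the event would then be counted in none of them. The error runs one way: it removes post-injection events from the safety summary of an investigational tracer. A pre-injection AE date is legitimate, since collection starts at consent, so nothing about it prompts a query.

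(b) The two definitions in 6.1.10 do not cover all drugs in use at injection. Treatment begun before the 30-day window and still being taken meets neither, even with complete dates. The table meant to show concomitant medication would omit long-standing therapy present at imaging.

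**Working it through.** **1. The SAP's own examples (12.1).** Intervals are end − start + 1, or onset − injection + 1.
- Start 31JAN2004, end FEB2004, printed ≥2. First-of-month gives 01FEB − 31JAN + 1 = 2.
- Start JAN2004, end 01FEB2004, printed ≥2. First-of-month gives 01FEB − 01JAN + 1 = 32. A start on 31JAN gives 2.
- Injection 31JAN2004, onset FEB2004, printed ≥2. First-of-month gives 01FEB − 31JAN + 1 = 2.

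All three fit one rule: the smallest interval compatible with the known parts. First-of-month dating fits the first and third but not the second, where the AE start date is partial.

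**2. One case under 6.1.4.2.** Injection on 15 January, true onset 16 to 31 January, day unknown. Imputed onset is 1 January. By 12.1(5), study day is 1 − 15 = −14, which is before injection. If injection is on the 1st, the imputed date equals the injection date and the problem does not arise.

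**3. Share misdated, given a missing day.** Take injection on each of 365 days and true onset on each of days 0 to 30: 365 × 31 = 11,315 pairs. A pair is misdated when onset is in the injection's month and injection is not on the 1st. A month of L days contributes L(L − 1)/2:
- seven 31-day months: 7 × 465 = 3,255
- four 30-day months: 4 × 435 = 1,740
- February: 378

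Total 5,373, and 5,373 / 11,315 = 0.475. Leaving out day 0 gives 5,020 / 10,950 = 0.458.

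**4. Expected events affected.** The documents give neither the number of AEs nor the rate of partial dates. Assume N post-injection AEs among the 45 participants and a fraction r with the day missing. Expected number = N × r × 0.475.

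| r | N = 10 | N = 20 | N = 40 |
|---|---|---|---|
| 2% | 0.09 | 0.19 | 0.38 |
| 5% | 0.24 | 0.47 | 0.95 |
| 10% | 0.47 | 0.95 | 1.9 |
| 20% | 0.95 | 1.9 | 3.8 |

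Nine of the twelve cells are below one event.

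**5. Medications, complete dates (days relative to injection).**
- Start −31 or −365, ongoing: neither table.
- Start −365, stopped +10: neither table.
- Start −20, ongoing: Table 14.1.7.2.
- Start −20, stopped −5: Table 14.1.7.1.
- Start +3: Table 14.1.7.2.

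**The case against.** **The flag is inferred.** A reader might infer that the SAP itself labels these events as not treatment-emergent. It does not: there is no written TEAE algorithm, and 6.1.3.1 defines the term by what happened to the participant. That limit stands. The literal result comes from joining 6.1.3.1 to the instruction in 6.1.4.2 that imputed dates govern assignment, and nothing in the SAP overrides that instruction.

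**Section 12.1 already departs from first-of-month dating.** This also stands. A reader might take two of the three examples as confirming 6.1.4.2, but those two fit the smallest-interval rule equally well, and the one example that separates the rules goes against 6.1.4.2. The opposite inference, that 12.1(5) protects the event, fails too. Its example has onset in the month after injection, and the inequality governs a displayed delay, not the TEAE flag.

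**Partial dates should be rare.** There is a call within 24 hours, a Day 30 visit, source verification and a five-working-day query turnaround (Protocol 15.1). Individual participation lasts at most about three months, so an onset known only to the year is improbable. This limits the size of the problem. Against it, no AE assessment is scheduled between the 24-hour call and Day 30, which leaves about four weeks to recall.

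**Nothing leaves the record.** The AE listings keep every event, SAEs and deaths also appear in Tables 14.3.2.1 and 14.3.2.2, and the drugs stay in Listing 16.2.4.4. Section 6.1.4.2 promises that all listings will mark incomplete dates, although the AE listing template shows no such column. So the harm is misclassification in summary tables, not lost data.

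**Part (b) is a different matter.** It is, and no planned analysis depends on that table. It is reported here as a separate gap.

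**Conclusion.** Both parts hold on the SAP's wording, at minor to should-fix level.

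(a) Read literally, 6.1.4.2 with 6.1.3.1 takes some post-injection AEs out of every AE frequency table, and 6.1.4.2 disagrees with 12.1(4) for a partial AE start date (32 days against ≥2). The 47% is conditional on the onset day being missing, and assumes onset even over days 0 to 30 and injection dates even over the year. It should not be read as almost half of all AEs being lost: under the assumed ranges the expected number is 0.09 to 3.8 events, and the true number is probably small. The primary endpoint is unaffected.

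(b) The gap in 6.1.10 is certain on its wording and needs no missing dates, but its size cannot be given. It is tempting to size it by the part of the eight-week screening window that lies beyond 30 days. That is not a valid magnitude, because drug start dates are not confined to the screening window.

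**What to change.** **SAP 6.1.4.2 and 12.1, one rule.** If the known parts of an AE onset date are compatible with onset on or after injection, impute onset as the later of the injection date and the first day of the known month (or year), and classify the AE as treatment-emergent. The exception is an AE whose end date as collected, before any imputation and judged on its known parts, shows that it ended before injection. A partial end date compatible with injection or later must not exclude the event, and should be imputed no earlier than the imputed onset. Otherwise keep the first-of-period rule. State this in 12.1 as the TEAE derivation and reconcile the examples in 12.1(4) and (5) with it.

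The end-date wording matters because 6.1.4.2 also sets partial end dates to the 1st. If the test used the imputed end date, an AE with both days missing could still be excluded: 5,373 of 11,315 pairs for same-day events, and 4,350 of 11,315 (38.4%) when the AE ends three days after onset. Judged on the end date as collected, none of the 11,315 is lost.

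**SAP 6.1.10.** Define Table 14.1.7.2 as any medication ongoing at injection or started after it, whatever its start date.

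**Cost.** SAP wording and derivation code only; no new data. Some pre-injection AEs with unknown onset day will be counted as treatment-emergent. With onset even over days −56 to −1, the upper bound is 5,373 / (365 × 56 = 20,440) = 26%, and fewer where an end before injection is recorded. That error is in the conservative direction for safety. The concomitant medication table becomes longer.

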6.1.5 Subject disposition

A listing of dates of assessments (relative day) and their study exposure will be presented by subject.

A summary table and a flow chart will be presented for each subject population presenting the number of subjects at each assessment procedure and identifying the number of subjects who withdrew over time.

6.1.6 Withdrawals

Discontinued subjects will be listed and a summary table of the number and percentage of subjects who withdrew from the study and the reasons for withdrawal will be presented for all screened subjects.

Version: 01 Page: **29 of 167**

6.1.7 Demographic and baseline characteristics

All demographic and baseline characteristics will be listed by subject. Summary statistics will be provided for demographic and baseline characteristics for FAS and Safety population (if different from FAS).

6.1.8 Medical and surgical history

Medical and surgical history will be coded using the Medical Dictionary for Regulatory Activities (MedDRA) Version 19.0.

Medical and surgical history will be listed on an individual basis, including Preferred Term (PT) and verbatim term; the listings will be sorted by subject.

A frequency table of the number and percentage of subjects will be provided for all medical and surgical history by primary SOC and PT for Safety population.

6.1.9 Subject compliance

After reconstitution and radiolabeling, ^{99m}Tc-rhAnnexin V-128 is administered as a single intravenous bolus of 350 MBq ± 10% at the imaging visit (Day 0). The administered dose recorded in the eCRF will not be the difference between the pre-injection dose and the post-injection residual dose but will be the decay corrected dose which takes into account the natural product half-life.

A listing will be presented for imaging product administration (dose, quality, date) by subject. Deviations from observed and scheduled times will be presented. Summary tables will be presented for all the continuous variables.

A listing will be presented for concomitant medications.

All the protocol deviations will be also listed by subject.

6.1.10 Prior and concomitant medications

Concomitant medications will be coded using ATC Drug Dictionary Version 2016.

Listings will be presented for ATC name (third level) and verbatim text. The listings will be sorted by subject, chronological start date, ATC name, verbatim text and active substance.

A frequency table of the number and percentage of subjects will be provided for concomitant medications by pharmacological subgroup and chemical substance for Safety population. Two different tables will report Prior Medications (the medications taken and stopped within 30 days prior the ^{99m}Tc-rhAnnexin V-128 injection) and Prior and Concomitant Medications (the medications

Version: 01 Page: **30 of 167**

started within 30 days prior the ^{99m}Tc-rhAnnexin V-128 injection and continued after the ^{99m}Tc-rhAnnexin V-128 injection and the medications started after the ^{99m}Tc-rhAnnexin V-128 injection).

